## 2.0 Objectives

The aim of this study is to examine using primarily short term measures and secondarily long term outcomes, the potential neuroprotective effects of the cooling+xenon combination when compared to cooling alone. We will examine the feasibility of recruiting earlier than previous trials, <3h for HT and <5h for starting xenon and assess what proportion of the eligible infants we can recruit. We will compare the short term biomarkers (aEEG recovery, MRI score, LDH and time to full feeds) in the two groups with those obtained previously in our randomised dataset (infants from CoolCap and TOBY) as well as the large group cooled since 1/12/2006 under the same protocol. In these groups of children we have both short term markers as well as Bayley outcome and have shown that our combined biomarkers has a PPV of 93%.

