## 2.1 Primary Endpoint

This is a randomised two group pilot study comparing;

- 1) xenon inhalation for 18 hours in combination with whole body cooling to 33.5 °C for 3 days, to
- 2) the established treatment of cooling the body down to 33.5 °C for 3 days.

Reference:	CH
Issue:	2
Revision:	3
Issue Date:	1 May 2013
Page	13 of 49

This will be applied in term newborn babies who display signs indicating moderate or severe brain injury following poor condition at birth.

Our hypothesis is that we may observe an enhanced neuroprotective effect of the xenon-cooling combination over cooling alone assessed initially by early outcome predictors. This will allow us to perform power calculations for a much larger neurological outcomes study of otherwise similar design. We have tested a combination of our early predictors (using our TOBY registry cooling data in 80 infants) against Bailey outcome at 18 months and found they have a positive predictive value of 94% in cooled infants

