#### **Additionally:**

We will do both short-term (14 days) and long-term (18 months survival) follow-up. In cooled babies we have shown that short-term predictors such as MRI at day 8 [2], time to normal aEEG [1] and peak LDH before 72h [4] predict long-term outcome with a positive predictive value of 84%, 92% and 80% respectively. In this study we will be able to examine these predictors for cooled babies receiving xenon treatment. By defining this relationship one can calculate the sample size for a large trial using short-term outcome.

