### **3.3 Justification of Design**

A human neonatal randomised pilot study comparing cooling (the established treatment) with the cooling+50% xenon combination is now the next logical step (see “Justification of Treatment” 3.4 below). This study is necessary for 3 reasons:

- 1) To validate our ability to recruit a large proportion of infants needing cooling as early as 3h of age and start xenon by 5hrs.
- 2) To examine the positive predictive value of our early outcome biomarkers proposed from the previous 100 cooled babies and compare with these.
- 3) Use these data for the statistical power calculations to estimate the group sizes for a larger randomised clinical trial of cooling+xenon. This approach follows a similar pattern to the early studies of cooling in neonates; a human technical feasibility/safety study [42] was performed using different target temperatures, followed by a study using a fixed temperature protocol for 72hours [20]. This protocol was then used in CoolCap [10], modified slightly for NICHD (National Institute of Child Health and Human Development)[43] and again used in TOBY, which were the 3 first large randomised controlled cooling trials. [12]

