**Additionally:**

We will do both short-term (14 days) and long-term (18 months survival) follow-up. In cooled babies we have shown that short-term predictors such as MRI at ~day 8 [2], time to normalisation of aEEG [1] and peak LDH before 72h [4] predict long-term outcome with a positive predictive value of 84%, 92% and 80% respectively. In this study we will be able to examine these predictors for cooled babies receiving xenon treatment. By defining these relationships one can calculate the sample size for a large trial using short-term outcome.

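### Comparing the markers' positive predictive value with earlier cohorts cannot show whether they remain valid, and 16 xenon infants cannot define the marker-outcome relationship that the protocol says can size a large trial

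*Protocol*

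**What the plan says.** Section 3.3 (Justification of Design) lists three reasons why the study is necessary. The second is "To examine the positive predictive value of our early outcome biomarkers", which were derived from 100 earlier cooled infants, and to compare the results with those infants. The third is to use the data for power calculations for a larger trial.

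The paragraph headed Additionally in section 3.2 states that MRI, time to normal aEEG and peak LDH "predict long-term outcome with a positive predictive value of 84%, 92% and 80% respectively". It continues: "In this study we will be able to examine these predictors for cooled babies receiving xenon treatment", and concludes: "By defining this relationship one can calculate the sample size for a large trial using short-term outcome". Section 7.5.4 repeats this with "By defining these relationships one can calculate the sample size for a large trial using short-term outcome".

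For the combined markers, section 2.0 says the investigators "have shown that our combined biomarkers has a PPV of 93" per cent. Section 2.1, citing 80 infants, says they "found they have a positive predictive value of 94% in cooled infants". PPV is the only accuracy measure quoted. No sensitivity, specificity or share of marker-positive infants is given.

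Section 9.1 limits the presentation to descriptive statistics and says that the study lacks power to test outcome.

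**The concern.** PPV mixes two things: how well the marker separates good from poor outcomes, and how common poor outcome is in the cohort. Comparing it between cohorts with different poor-outcome rates does not isolate the marker's validity. The protocol's cohorts do differ in that rate. Entry here also differs from earlier practice (cooling by 3 h rather than 6 h, per the Overview), so the rate may differ again.

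The second problem is size. PPV is a proportion among marker-positive infants only, and in one arm of 16 there will be few of them. At stake is a large trial sized on a short-term outcome whose link to 18-month outcome under xenon is taken as established by this pilot.

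**Working it through.** **Inputs from the protocol.** 16 infants per arm (3.3, 9.1). Poor outcome when cooled: 39% locally and 48% in TOBY (1.2), 51% across the large trials (1.2, 3.4). PPV: MRI 84%, aEEG 92%, LDH 80% (3.2); combined 93% or 94% (2.0, 2.1). The Protocol Summary attributes the MRI figure to cooled TOBY infants.

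**Assumptions.** Sensitivity 0.6 to 1.0. The MRI PPV arose at 48%, and the aEEG and LDH PPVs at 39%. Relative risk of poor outcome under xenon 0.75 or 0.50. None of these is stated in the protocol.

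**The plan's own figures.** The local 39% agrees with the stated relative reduction: (63 - 39)/63 = 38%. The sample size in 3.3 is a rule of thumb of 12 per group plus 8 infants: 2 x 12 + 8 = 32, or 16 per group. That rule concerns the precision of a mean and a variance. No figure is given for estimating a PPV, so there is none to reproduce.

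**1. PPV moves with the poor-outcome rate.** Likelihood ratio LR = [PPV/(1 - PPV)] / [p/(1 - p)]; at a new rate p', PPV' = LR x odds' / (1 + LR x odds').

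- MRI: LR = 5.25/0.923 = 5.69. At 39%, odds' = 0.639, so PPV' = 3.64/4.64 = 78%. That is about six points lower with the same accuracy and no xenon.

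**2. Xenon effect, accuracy held fixed.** The local 39% becomes 29.25% (relative risk 0.75, odds 0.413) or 19.5% (0.50, odds 0.242).

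| Marker | LR | PPV at 39% | at 29.25% | at 19.5% |
|---|---|---|---|---|
| MRI | 5.69 | 78% | 70% | 58% |
| aEEG | 17.99 | 92% | 88% | 81% |
| LDH | 6.26 | 80% | 72% | 60% |

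**3. Xenon effect wholly through the marker.** The risk of poor outcome given marker status stays fixed, so PPV is unchanged and fewer infants are positive. For aEEG with sensitivity 0.8:

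- Share positive: 0.39 x 0.8/0.92 = 0.339, or 5.4 of 16.
- Risk if negative: 0.39 x 0.2/0.661 = 0.118.
- At relative risk 0.75: share positive = (0.2925 - 0.118)/(0.92 - 0.118) = 0.218, or 3.5 of 16.
- At relative risk 0.50: (0.195 - 0.118)/0.802 = 0.096, or 1.5 of 16.

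PPV remains 92% throughout.

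**4. Number of marker-positives without a xenon effect.** Count = 16 x rate x sensitivity / PPV.

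- At 39%: from 6.24 x 0.6/0.94 = 4.0 to 6.24 x 1.0/0.80 = 7.8; 6.2 if sensitivity equals PPV.
- At 51%: from 8.16 x 0.6/0.94 = 5.2 to 8.16/0.80 = 10.2.

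**5. Precision (exact Clopper-Pearson 95% intervals).**

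| Correct / positive | Interval |
|---|---|
| 4/4 | 40-100% |
| 5/6 | 36-99.6% |
| 6/6 | 54-100% |
| 7/8 | 47-99.7% |
| 9/10 | 56-99.7% |
| 11/12 (arms pooled) | 62-99.8% |

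Each interval contains every reference PPV from 80% to 94%. If the true PPV under xenon were 60% and six infants were positive, the interval would exclude 84% only when two or fewer were correct (probability 18%). It would exclude 92% only when three or fewer were correct (46%).

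**6. What would be needed.** For a half-width of 10 points, n = 1.96² x PPV x (1 - PPV)/0.1²: 62 positives at 80%, 52 at 84%, 29 at 92%. If 39% of infants are positive, that is about 73 to 158 infants per arm.

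**The case against.** - **A reader might infer that PPV must fall if xenon works, so that the comparison penalises an effective treatment.** The documents do not support this. The markers are read largely after treatment starts, and the protocol's hypothesis is that benefit will show in them. Under step 3 PPV does not move. A fall is possible but not implied.
- **No decision hangs on PPV.** This stands. The protocol sets no PPV threshold and no rule for declaring a marker invalid. Reason 2 in 3.3 does not name xenon, and 9.1 describes the historical comparison for the cooled-only group. The xenon link comes from 3.2 and 7.5.4. The shift from 84% to 78% in step 1, however, arises among cooled-only infants.
- **The limits are already conceded.** Section 9.1 says descriptive only and no power for outcome. That tempers the point, but it does not withdraw the sentences in 3.2 and 7.5.4, which still present the relationship as something the pilot will define and use.
- **The pilot can inform sizing without PPV.** This also stands. Means and variances of continuous markers are ordinary planning inputs, and the 12-per-group rule addresses them. A reader might infer that the pilot cannot help size a later trial at all, which would go too far.
- **Other accuracy measures are no better at this size.** They will be just as imprecise, and they can also shift: in step 3 at relative risk 0.75, sensitivity falls from 0.80 to 0.218 x 0.92/0.2925 = 0.68. They belong beside PPV, not in its place.

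**Conclusion.** The point holds in two limited parts.

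First, a PPV that differs from, or matches, that of earlier cohorts does not by itself show whether a marker has lost or kept its validity. On the protocol's rates, the MRI figure alone would move from 84% to about 78% with unchanged accuracy, taking 48% as the rate behind the 84%. The combined reference value is not settled either: 93% or 94%, with 80 infants cited in 2.1 and 100 in 3.3.

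Second, the marker-outcome relationship under xenon cannot be defined with 16 infants. About 4 to 8 marker-positives are expected at 39% poor outcome and up to 10 at 51%, fewer if xenon acts through the marker. Even 6 of 6 correct leaves an interval of 54-100%. These counts rest on the assumed sensitivity of 0.6 to 1.0. The conclusion is the same across that range.

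This is a correction to a stated aim and to how its result is read. It does not undermine the feasibility purpose of the pilot.

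**What to change.** In sections 3.2, 3.3 and 7.5.4:

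1. State that sensitivity, specificity and likelihood ratios will be reported alongside PPV, by arm, with exact intervals, together with the poor-outcome rate of each cohort compared, all labelled descriptive.
2. State that a difference in PPV from historical cohorts will not be read as a change in marker validity.
3. Replace the sentence claiming that defining the relationship yields a sample size with: the pilot gives only descriptive data on marker performance under xenon; the means and variances of the short-term markers may inform the sizing of a later trial.
4. Name one reference cohort and one combined PPV.

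The cost is a few sentences and a small table. The stated aim becomes less ambitious, and the added measures will also be imprecise.

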#### **Group size calculation**

Sixteen babies will be recruited into each group (cooling+xenon vs cooling alone) at random. The cooling will be applied as standard treatment if cooling criteria are met. Addition of xenon in combination with this underlying cooling will take place in the group randomised to receive cooling + xenon.

For pilot studies of this type the recommendation is a sample size of 12 per group. The justifications for this sample size are based on

- i) Feasibility – allows convenient block sizes, for example our intention for a data review committee to review data sets at block intervals of 4 neonates.
- ii) Precision about the mean – little additional precision to be gained by having a larger group size than 12 [44].
- iii) Precision about the variance – little additional precision to be gained by having a larger group size than 12 [44].

Reference [44] presented in full in Appendix 10.

The first 15 neonates were recruited in a period where the xenon ambulance transfer system was not ready for use. The clinical staff employed to recruit and deliver the xenon in the ambulance needed time to gain experience using the system before using it independently away from the base hospital without the supervision of [name]. This has led to a similar number of babies which we failed to recruit (due to the time limitation) as the number recruited to

Reference:	CH
Issue:	2
Revision:	3
Issue Date:	1 May 2013
Page	25 of 49

xenon. We therefore wish to recruit a further 8 babies to assess the feasibility to recruit, more reliably, consecutive babies fulfilling the entry criteria within the confines of the protocol

### 3.4 Justification of Treatment / Procedure

Even with the best available treatment (hypothermia) infants with HIE have a considerable risk of death or disability of 51%. This study offers an additional treatment which has been shown in two animal species to improve (double) brain protection over and above the protection from cooling alone. Our large animal trial of Xenon-hypothermia in piglets conducted with a delivery system of the same design as proposed for this study has very recently concluded with a very positive outcome [15] supporting the result we found in rats, ie adding xenon to HT doubles the neuroprotection [14, 17].

This equipment has recently been used in 14 human neonates during our recently completed human feasibility/safety study (Appendix 4).

## 4.0 Study Therapies

### 4.1 Test Article: Description

#### Overview

The neonatal xenon breathing device (NXBD) is a gas delivery circuit with some similarities to an anaesthesia circuit that is temporarily placed between a standard mechanical ventilator and the tracheal tube of a neonate to deliver xenon as a therapy in the breathing gas. It is designed for use in neonates who already require mechanical ventilation in this manner on a neonatal intensive care unit. Its purpose is to provide a gas mixture to the lungs that contains not only an appropriate oxygen concentration to maintain life, but also to provide a concentration of up to 50% xenon in this mixture. The reason for this is that xenon shows great promise as a neuroprotectant and has been shown to reduce neurological damage in both small and large laboratory *in-vivo* models of neonatal hypoxia-ischaemia (birth asphyxia for example). By re-circulating the exhaled gases after removal of carbon dioxide then, as the uptake of xenon by a neonate is very low and the system does not "vent" any exhaled gas to the environment, it provides a very economical method of xenon delivery. Such economy will be essential for any future clinical use of xenon as this gas is both limited in availability and extremely expensive at approximately £20/litre. While the (minimal) xenon uptake is replaced manually by the operator, the breathing device automatically adds oxygen as required to match metabolic uptake by the patient. This is not achieved by complex sensors and electronics but by a straightforward mechanical mechanism for reliability. Furthermore, if xenon replacement is stopped, the inspired oxygen concentration will tend to very slowly increase i.e. it will not fall as the patient consumes oxygen from the circuit – these are both inherent safety features. The most important and intuitive safety feature is that in the event of any problem, the mechanical ventilator patient connector can be disconnected from the breathing system and reconnected directly to the tracheal tube of the neonate, instantly restoring normal ventilation and also allowing any xenon to very rapidly dissipate from the tissues of the neonate.

### 4.2 Test Article: Principles of Operation

If no fresh oxygen is supplied to a conventional anaesthesia circle system the patient will consume all oxygen present until a hypoxic mixture develops. Therefore in a closed circle system, fresh gases must be added at a rate exactly matching patient uptake of each gas. There are various ways to achieve this. In the simplest of closed underwater diving systems, the user will breathe pure oxygen around a circuit similar to an anaesthesia circle. In time, by metabolic oxygen consumption, the reservoir bag will completely collapse part-way through an inspired breath. At this point, by continued inspiratory effort, a demand valve on an attached oxygen cylinder will open, providing the missing volume of oxygen to complete the inspiration phase. If we now imagine this circle to contain a mixture of xenon (slow patient uptake) and oxygen (metabolic uptake) a different situation develops. It can be envisaged that substitution of these two uptake volumes with pure oxygen at each end-inspiration would produce a slowly increasing inspired oxygen fraction ( $FiO_2$ ).

[figure not shown]
We have incorporated these concepts into a ventilator driven closed circuit where a standard Neonatal Intensive Care Unit (NICU) ventilator, set to deliver 100% oxygen in each breath to the circuit, provides not only the motive power but also, via a special volume substitution valve, the required oxygen replenishment in place of the demand valve in the diving example.

Reference:	CH
Issue:	2
Revision:	3
Issue Date:	1 May 2013
Page	26 of 49

When delivering a xenon/oxygen mixture there would then be a background tendency for the  $\text{FiO}_2$  to slowly increase while the inspired xenon concentration decreases at a similar rate. This provides a degree of hypoxic mixture protection without use of oxygen sensor and computer software controlled electronic valves. In other words, adequate oxygen supply, the most critical function of any breathing system, is not entirely dependent on correct functioning of sensors, software and electronic dosing valves, as would be the case with an electronically controlled system.

[figure not shown]
Against this inherent safety feature of a very slowly increasing the  $\text{FiO}_2$ , and the minimal xenon uptake of a neonate from the closed loop circle breathing system, xenon can then be delivered to the circle in small volumes under manual control to offset this trend, replacing the minimal patient xenon uptake.

The design of a breathing circuit to achieve these design aims is described in Figure 1.

**Figure 1a.** Diagram of the breathing system

Reference:	CH
Issue:	2
Revision:	3
Issue Date:	1 May 2013
Page	27 of 49

**Figure 1b.** Views of breathing system (without hoses)

[figure not shown]
The xenon delivery system is designed to be fitted between a conventional neonatal intensive care unit (NICU) mechanical ventilator (SLE 2000, SLE, South Croydon, UK) and the tracheal tube. The latex-free bag in the lower chamber has a volume of 500ml, larger than a neonatal tidal volume, providing free space to accommodate added xenon bolus volumes without overspill. The removable soda-lime canister has a volume of 510ml permitting long periods of ventilation without replacement.

In this design, a small aliquot of oxygen enters the closed circle upper part of the circuit at each end-inspiration from a lower bag-in-bottle chamber (where it is present as the driving gas from the ventilator) via a dedicated oxygen substitution valve. Modern NICU ventilators maintain a bias gas flow throughout the breathing cycle. At end-expiration this displaces any residual CO2 from the "Y" connector reducing CO2 rebreathing. However with a closed circuit, the absence of a bias flow combined with small neonatal tidal volumes means that an efficient self-closing, leak free, low opening pressure inspiratory valve was required to prevent rebreathing. A unidirectional valve performs this function. A similar valve design is used as the expiratory valve and as the oxygen substitution valve.

Gas delivery to breathing system:

Oxygen consumed by the neonate from the circle is replaced automatically via the oxygen substitution valve as described above and in Figure 1. The slow-rising FiO2 tendency (a condition of inherent safety against the development of accidental hypoxic mixtures) is then deliberately offset by occasional manual delivery of xenon boluses to the circle, so maintaining the target xenon concentration – the combination of closed circuit, low patient weight and low xenon uptake making these xenon doses very infrequent (<200ml Xe per hour from laboratory data).

Reference:	CH
Issue:	2
Revision:	3
Issue Date:	1 May 2013
Page	28 of 49

[figure not shown]

**Figure 1c.** Details of exact medical components used to construct the hoses of the breathing circuit, with part numbers. Hoses, humidification chamber and connectors all manufactured by Armstrong Medical Ltd, UK

Reference:	CH
Issue:	2
Revision:	3
Issue Date:	1 May 2013
Page	29 of 49

We have previously delivered xenon using high pressure xenon cylinders with electronic valves actuated by both computer and manual control. After using servo control in the past we realised that due to the slow uptake of xenon, manual addition of xenon boluses would not be particularly onerous facilitating this more straightforward design devoid of any computer control systems.

The manual xenon dosing mechanism is designed to function at ambient pressure for additional simplicity and safety, so eliminating any risk of the circle “flooding” with xenon due to a cylinder/regulator/electronic malfunction (Figure 2).

**Figure 2.**

A flexible bulb and valve arrangement allows manual addition of ~50ml xenon boluses to the circle breathing system, from a previously filled reservoir bag of xenon at ambient pressure. These are added to the expiratory limb of the circuit to allow maximum mixing with existing gases in the circle before entering the lungs. The small flexible bulb volume of 50ml was selected because the small bulb volume combined with its slow refill properties further aids even gas mixing, it being impossible to rapidly add a large xenon bolus. Erring on the side of caution, our circuit was primed with oxygen. The xenon/oxygen monitors are constantly observed as in the conduct of a conventional anaesthetic. Deviations in xenon concentration of more than 2-4% from target are corrected by the operator adding xenon to the circuit, each 50ml bolus typically producing a 2% increase in xenon concentration. These corrections offset the inherent tendency of this circuit design to generate a very slowly increasing oxygen concentration ( $O_2$  + minimal Xe consumptions being replaced with equal volume of oxygen via substitution valve).

The overall design aims were that this breathing system should (i) be driven by a standard NICU ventilator, (ii) have inherent hypoxic mixture prevention properties not dependent on electronics (iii) provide the user with the most intuitive treatment reversal method; reconnection of the neonate directly to the NICU ventilator. It performs all these functions.

